#### 6.1.12 Visit 9, Week 48 (Local or Surgical Site)

The following assessments will be performed for ALL subjects unless otherwise specified:

- Concomitant medication
- Vital signs
- Biochemistry/haematology
- [REDACTED]
- [REDACTED]
- [REDACTED]
- AEs
- Ophthalmic examination
- CFP
- FAF
- OCT macula
- [REDACTED]
- [REDACTED]
- [REDACTED]
- BCVA using ETDRS
- LLVA using ETDRS for LLD
- MNRead
- VFQ-25
- FRI Index
- OCT-A and/or FA if clinically indicated (if a subject converts to wet AMD)
- [REDACTED]
- [REDACTED]
- [REDACTED]

#### 6.1.13 Visit 10, Week 72 (Local or Surgical Site)

The following assessments will be performed for ALL subjects unless otherwise specified:

- Concomitant medication
- Vital signs
- Biochemistry/haematology
- AEs
- Ophthalmic examination

- CFP
- FAF
- OCT macula
- [REDACTED]
- [REDACTED]
- BCVA using ETDRS
- LLVA using ETDRS for LLD
- MNRead
- VFQ-25
- FRI Index
- OCT-A and/or FA if clinically indicated (if a subject converts to wet AMD)
- [REDACTED]
- [REDACTED]

#### **6.1.14 Visit 11, Week 96/End of Study and Early Termination Visit (Local or Surgical Site)**

The following assessments will be performed for ALL subjects unless otherwise specified:

- Concomitant medication
- Vital signs
- Biochemistry/haematology
- [REDACTED]
- [REDACTED]
- [REDACTED]
- [REDACTED]
- AEs
- Ophthalmic examination
- CFP
- FAF
- OCT macula
- [REDACTED]

- BCVA using ETDRS
- LLVA using ETDRS for LLD
- MNRead
- VFQ-25
- FRI Index
- OCT-A and/or FA if clinically indicated (if a subject converts to wet AMD)

#### 6.1.15 Unscheduled Visit

If clinically indicated, subjects may need to return to the site for an unscheduled visit. The Investigator will perform assessments considered to be appropriate for the Subject, considering the reason behind the need to arrange an unscheduled visit. These results should be recorded in the subject's medical notes and eCRF.

## 7 STUDY ASSESSMENT

### 7.1 Demographic and Screening Assessments

#### **Informed Consent Procedure**

The informed consent process will be conducted prior to performing any study procedures.

Subjects entered into the study must have genotyping and serum CFI evaluation performed by a Sponsor-approved laboratory, either through participation in a previous Gyroscope sponsored study or during the EXPLORE screening period. Informed consent will include permission for genotyping (genotyping and serum CFI evaluation are not required for subjects who have these from another Gyroscope study) and a consent from each subject or legal representative to enrol into EXPLORE and undergo ophthalmic and clinical assessments to determine eligibility for inclusion in the study. Data from subjects screened in another Gyroscope sponsored study at the same Investigative site as EXPLORE may be used to fulfil the screening and eligibility requirements for this study. This is only permissible if the screening data is collected within the screening period specified in the clinical protocol. Should subjects fail to meet the eligibility for EXPLORE, they will be classed as Screen Failures for this study and may be considered for entry into another Gyroscope sponsored study.

It is the responsibility of the Investigator, or a suitably qualified person delegated by the Investigator to obtain written informed consent from each subject. The Investigator or designee will explain that the subject is under no obligation to enter the study and that they may withdraw at any time during the study, without having to give a reason.

A copy of the signed ICF will be given to the participant. The original signed form will be retained at the study site.

#### **Subject Eligibility**

It is the responsibility of the Investigator, or a suitably qualified person delegated by the Investigator, to confirm the eligibility of each subject for the study. Review and confirmation of eligibility is to be documented in the subjects' medical records.

#### **Demographics**

Subject demographics, including year of birth, race, ethnicity, sex, at baseline will be captured.

#### **Medical/Surgical History**

Prior medical history (including all ocular history) will be reviewed and recorded in the eCRF. This will comprise of (and be updated throughout the study):

- All current and prior ocular medical and surgical history
- All current and prior significant general medical and surgical history
- Pertinent family (e.g., related parents and children) and social history

For those subjects who have not previously been genotyped, and who fulfil Inclusion Criteria 1, 2, and 3, consent for genotyping and a genotyping sample should be obtained prior to performing any other screening assessments (Visit 1). Where necessary, and to help fulfill this requirement, Visit 1 can occur over a number of days.

## 7.2 Concomitant Medication [REDACTED]

### 7.2.1 Concomitant Medication

All concomitant medication will be reviewed and recorded, including:

- current medication use
- any drug allergy or contraindication to steroids

[REDACTED]  
[REDACTED]  
[REDACTED]

## 7.3 Ophthalmic Assessments

Details of the required assessments will be provided in the Central Imaging Manual.

Camera equipment used at investigative sites will be required to meet the specifications of the CRC as specified in the Central Imaging Manual.

### 7.3.1 Ophthalmic Examination

Ophthalmological examinations in both eyes will be performed as follows: anterior segment examination via slit lamp biomicroscopy, intraocular pressure via Goldmann applanation tonometry (GAT) or a Tono-Pen®, posterior segment and fundus examination via dilated indirect ophthalmoscopy. Ocular inflammation will be assessed.

Slit lamp will be conducted on both eyes. The eyelids, cornea, conjunctiva, anterior chamber, iris/pupil and lens should be evaluated. Findings will be graded as normal, abnormal non-clinically significant, or abnormal clinically significant. Cataract will be graded using the AREDS clinical lens grading system [Appendix 17.1]. Intraocular pressure should be assessed using the same method (GAT or Tono-Pen®) throughout the study, regardless of method chosen.

Dilated indirect ophthalmoscopy will assess the vitreous, macula, choroid, optic nerve, retina and cup- to-disc ratio of both eyes. Findings will be graded as normal, abnormal non-clinically significant, or abnormal clinically significant.

### 7.3.2 Pre-surgical Ocular Safety Check

A pre-surgical ocular safety check should be performed to verify there are no new ocular adverse events that would halt surgery. Pre-surgical ocular safety checks should be performed as per local procedures and/or at the discretion of the Investigator assessing the subject.

### 7.3.3 Colour Fundus Photography

CFP of the fundus of both eyes will be performed by certified technicians following pupil dilation. All fundus photographs will be sent by the sites to the CRC for review; the CRC will transfer the data to the data management group and/or Independent Statistics Centre (ISC). For complete technical specifications for fundus photography, refer to the Central Imaging Manual (which will include procedures from the CRC regarding how measurements are to be taken).

#### 7.3.4 Fundus Autofluorescence

To assess changes in the area of GA, FAF will be performed for both eyes.

All FAF images will be performed by certified technicians at the site after dilation of the subject's pupil and sent to a CRC for review; the CRC will transfer the data to the data management group and/or ISC. For complete technical specifications for FAF, refer to the Central Imaging Manual (which will include procedures from the CRC regarding how measurements are to be taken).

#### 7.3.5 Optical Coherence Tomography ( [REDACTED] Macula)

OCT is a method of using low-coherence interferometry to determine the echo time delay and magnitude of backscattered light reflected off an object of interest. This method can be used to scan through the layers of a structured tissue sample such as the retina with very high axial resolution (3 to 15  $\mu\text{m}$ ), providing images demonstrating three-dimensional structure. Because of the unique optically clear pathway through the eye, OCT has been used most extensively for imaging disorders affecting the retina.

OCT will be performed for both eyes. OCT images will be taken by certified technicians at the site after dilation of the subject's pupil. All OCT scans will be submitted by the sites to a CRC where the scans will be evaluated; the CRC will transfer the data to the data management group and/or ISC. For complete technical specifications for OCT, refer to the Central Imaging Manual (which will include procedures from the CRC regarding how images are to be taken).

[figure not shown]
#### 7.3.6 Optical Coherence Tomography-A

OCT-A allows for non-invasive evaluation of retinal and choroidal vascular abnormalities that is useful as a diagnostic tool for Investigators to identify CNV which is an eligibility exclusion criterion. Other imaging modalities as described in the Central Imaging Manual may also be utilised to assess for CNV. OCT-A may be performed as clinically indicated during the course of the study, for example, if a subject converts to wet AMD.

#### 7.3.7 Fluorescein Angiography

Fluorescein angiography is used to examine the circulation of the retina and choroid using a fluorescent dye and a specialised camera. Sodium fluorescein is added into the systemic circulation, the retina is illuminated with blue light at a wavelength of 490 nanometres, and an angiogram is obtained by photographing the fluorescent green light emitted by the dye.

Fluorescein angiography may be performed to assess CNV to confirm eligibility and as clinically indicated during the course of the study, for example, if a subject converts to wet AMD.

### 7.3.9 Visual Acuity Check

A visual acuity check using a Snellen chart (near card is permissible) must be performed pre-surgery on the study eye if >4 weeks have elapsed between BCVA with ETDRS and surgery. If Snellen result is >2 lines (BCVA equivalent to 10 letters), worse than the previous BCVA ETDRS score, then a BCVA with ETDRS assessment must be repeated. If the BCVA with EDTRS results is  $\leq 2$  lines worsened compared to the previous BCVA with ETDRS, record the subject's vision in the eCRF and surgery can proceed. If the repeat BCVA with EDTRS check remains >2 lines (BCVA equivalent to 10 letters) worsened, surgery must be postponed pending discussion and approval by the Sponsor Medical Monitor.

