### 6.1.3 Visit 2, Day 1 (Surgical Site)

Visit 2 will only apply to subjects randomised to GT005.

This visit will be performed at a centralised surgical site and will be split in three parts: pre-surgery, surgery, and post-surgery assessments.

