#### 6.1.3.1 Pre-surgery (Surgical Site)

Pre-surgical assessments will include any local requirements of the surgical site. Pre-surgery is defined as the time between randomisation and surgery. The following assessments are required pre-surgery:

- Medical/surgical history
- Concomitant medication
- Pregnancy test
- Vital signs
- AEs
- [REDACTED]
- [REDACTED]
- Pre-surgical ocular safety check to verify there are no new ocular adverse events that would halt surgery
- Snellen visual acuity (refer to Section 7.3.9)

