### 2.1.1.2 Baseline and post-Baseline

*Baseline* (Day 1) is defined as

- the day following randomization for subjects randomized to untreated control
- the day of successfully receiving GT005 administration for subjects randomized to GT005
- or the latest surgery date for subjects who were randomized to GT005 but failed to receive GT005 administration on the first attempt to surgery (if applicable)

The baseline value for efficacy and safety variables is the last available value (scheduled or unscheduled) collected prior to the date of *Baseline*, or on the date of *Baseline* but prior to the time of GT005 administration for GT005 treatment groups.

All data collected after the date of *Baseline* are defined as post-baseline. The *study day* for a baseline or post-baseline scheduled or unscheduled visit is defined as:

$$\text{Study day} = \begin{cases} (\text{Date of visit}) - (\text{Date of randomization}) & \text{Untreated} \\ (\text{Date of visit}) - (\text{Date of treatment administration}) + 1 & \text{GT005} \end{cases}$$

The *study day* for a scheduled or unscheduled visit before baseline is defined as

$$\text{Study day} = \begin{cases} (\text{Date of visit}) - (\text{Date of randomization}) - 1 & \text{Untreated} \\ (\text{Date of visit}) - (\text{Date of treatment administration}) & \text{GT005} \end{cases}$$

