### 2.7.3 Loss in best corrected visual acuity

The number and the percentage of subjects who lost  $\geq 15/\geq 30$  letters in BCVA from baseline up to Week 96 will be presented for the study eye and the fellow eye. Missing data will not be imputed.

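### A pre-surgery ETDRS repeat made only when acuity looks worse, and only in GT005 subjects, can become the BCVA baseline and tends to understate vision loss in that arm

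*Protocol*

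**What the plan says.** **The check.** Protocol Section 7.3.9 says that a Snellen check "must be performed pre-surgery on the study eye if >4 weeks have elapsed between BCVA with ETDRS and surgery". If the result is more than two lines (10 letters) "worse than the previous BCVA ETDRS score, then a BCVA with ETDRS assessment must be repeated". A stable or better Snellen result prompts no repeat under this rule. If the repeat is no more than two lines worse, the instruction is to "record the subject's vision in the eCRF and surgery can proceed". If it is still more than two lines worse, "surgery must be postponed pending discussion and approval by the Sponsor Medical Monitor".

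**Who has it.** Section 6.1.3.1 lists the check among the pre-surgery assessments of Visit 2, and Section 6.1.3 states "Visit 2 will only apply to subjects randomised to GT005". The untreated-control schedule (Table 2) has no counterpart. Control Day 1 is the day after randomisation, so controls have no waiting period that matches the wait for surgery.

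**The baseline.** SAP Section 2.1.1.2 says the baseline value for efficacy and safety variables "is the last available value (scheduled or unscheduled) collected prior to the date of" Day 1. It makes no exception for this repeat.

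**Where it is used.** SAP Section 2.6.2 (item 4.a) models change from baseline in BCVA with baseline BCVA as covariate. SAP Section 2.7.3 counts subjects who lost at least 15 or 30 "letters in BCVA from baseline up to Week 96", without adjustment. No other BCVA baseline is planned.

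**The concern.** A repeat made only after an apparent drop selects two kinds of subject: those whose screening score was high by chance, and those who really declined while waiting. Replacing the screening score with the repeat removes both from GT005 change from baseline. Neither is removed in controls. The choice of baseline then depends on a post-randomisation reading in one arm and one direction, so randomisation does not balance it.

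At stake are a secondary efficacy endpoint and a descriptive safety table. Both would make the arm that had surgery look somewhat better on vision than it is.

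**Working it through.** The plan states no figure on this point, so there is none to reproduce.

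**1. Routes to a repeat BCVA before Day 1**

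| Route | Arm | Depends on worsening? |
|---|---|---|
| Section 7.3.9, more than 4 weeks since last ETDRS | GT005 only | Yes |
| Screening longer than 8 weeks (Section 6.1.1; footnote 1 of Tables 1 and 2) | Written for both | No |
| Rescreening (Section 4.3) | Both | No |
| Deferred administration, more than 12 weeks from screening (Section 6.1.3.2) | GT005 | No |

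Only the first selects on a worse reading. Because an unconditional repeat is due after 8 weeks, the selective trigger acts mainly between 4 and 8 weeks.

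**2. Model.** With true acuity T at screening:

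- screening ETDRS: X1 = T + e1
- true acuity before surgery: T2 = T + d
- Snellen: S = T2 + s
- repeat ETDRS: X2 = T2 + e2
- GT005 baseline: B = X2 if S < X1 − 10, otherwise X1
- control baseline: X1
- arm shift = mean(X1 − B) = share triggered × mean fall when triggered

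The SDs and the drift d are assumptions. The first results assume that every GT005 subject is past 4 weeks and that every repeat becomes baseline.

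| ETDRS SD / Snellen SD / drift mean (SD) | Triggered | Mean fall if triggered | Arm shift | Arm shift if 50% are past 4 weeks | Arm shift + mean drift |
|---|---|---|---|---|---|
| 3 / 5 / 0 (2) | 5.2% | 4.3 | 0.23 | 0.1 | +0.23 |
| 4 / 6 / 0 (3) | 10.0% | 5.6 | 0.56 | 0.3 | +0.56 |
| 5 / 7 / 0 (3) | 13.6% | 6.0 | 0.81 | 0.4 | +0.81 |
| 4 / 6 / −1 (4) | 13.8% | 7.2 | 0.99 | 0.5 | −0.01 |
| 5 / 8 / −1 (4) | 19.0% | 6.7 | 1.27 | 0.6 | +0.27 |

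The last column is the bias measured against true change since Day 1; positive values flatter GT005. For example, 1.27 − 1.00 = +0.27. A screening baseline gives 0 in the first three rows and −1.0 in the last two.

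**3. Repeats still more than two lines worse.** These are 9 to 33% of triggered subjects in these settings. If none becomes baseline, the arm shift is 0.17 to 0.38 letters.

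**4. Direction in individuals.** In these settings 11 to 19% of triggered repeats are higher than the screening score. The fall is an average.

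**5. Baseline covariate.** A wider run used ETDRS SD 3 to 7, Snellen SD 5 to 10, Snellen reading 0 to 5 letters low, 50 to 100% past 4 weeks, and drift 0 to −1. It gave an arm shift of 0.07 to 1.7 letters, of which 0.07 to 1.5 remained after baseline adjustment. The covariate does not remove it.

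**6. Letter-loss table.** If baseline falls by k letters, a subject must lose 15 + k letters from the screening score to be counted. With k of 4 to 7, that is 19 to 22 letters. The wider run assumed true change after Day 1 of mean −5, SD 10, and no treatment effect. The proportion losing at least 15 letters was understated by about 0.2 to 4.5 percentage points. At ETDRS SD 5, Snellen SD 7, no drift and everyone past 4 weeks, it was 19.2% against 20.8%. If repeats still more than two lines worse never become baseline, the understatement is about 0.3 to 0.9 points.

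**7. LLD.** LLD is BCVA minus LLVA (Section 7.3.11), and Section 7.3.9 repeats only BCVA. If baseline LLD is built from each component's last value, a triggered subject's repeat BCVA is paired with an older LLVA.

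**The case against.** **The later value is nearer Day 1, so it is the better baseline.** This has force. GT005 visits are counted from surgery, and decline before Day 1 is not change since Day 1. In the two settings with drift, the last-value rule is nearly unbiased on that measure (−0.01 and +0.27), while a screening baseline carries the full −1.0. The largest figures should therefore not be read as pure bias. But the rule updates only subjects who seem to worsen, so any offset is accidental, and with no mean drift all of the 0.23 to 0.81 is bias. Controls also keep their own decline between screening and Day 1, so the arms differ only by decline after randomisation.

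**Controls are re-measured too.** Correct for the repeat after 8 weeks. A reader might infer that only GT005 subjects can have BCVA repeated; the documents do not support that. The 8-week repeat does not depend on worsening, however, so it narrows the window without cancelling the selection.

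**Large drops postpone surgery.** True, and this brings the shift down to about 0.2 to 0.4 letters if such repeats never become baseline. Dosing remains possible after approval, and the SAP does not say which value then serves.

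**Little hangs on it.** BCVA is a secondary endpoint in an exploratory study with no inferential testing planned (Protocol Section 9.4.2), which the SAP Introduction says is being stopped after a futility analysis. This limits the importance of the point but does not answer it.

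**A footnote may qualify the check.** The Table 1 entry carries a footnote whose text is not visible in the public copy. Section 7.3.9 is complete without it.

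**Conclusion.** The concern holds. As written, the plan gives the GT005 arm a baseline that depends on apparent worsening and gives controls none. On average this lowers GT005 baseline BCVA and tends to understate vision loss in the model and the letter-loss table.

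The mechanism rests on the text. The size rests on assumed measurement error, drift and timing, none of which the documents supply. A fair statement is an arm-mean shift of about 0.1 to 1.3 letters, about half the full-exposure figures if only 50% of GT005 subjects are past 4 weeks, and about 0.2 to 0.4 if repeats still more than two lines worse never become baseline. Part of the upper end is real decline before Day 1.

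Two stronger readings should be resisted. Not every triggered GT005 baseline is lowered, since some repeats come out higher. And the primary endpoint is not touched: Section 7.3.9 repeats BCVA, not FAF. The point is worth correcting but is unlikely by itself to change the study's conclusion.

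**What to change.** In SAP Section 2.1.1.2:

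- Exclude ETDRS repeats triggered by the Section 7.3.9 worsening check from the baseline for BCVA and LLD.
- Use the last BCVA obtained under a rule that does not depend on worsening: screening, or the unconditional repeat after 8 weeks.
- For LLD, take BCVA and LLVA from the same date.
- List the triggered repeats, and report the BCVA model and the letter-loss table with the current last-value baseline as a sensitivity analysis.

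This removes the selection on worsening. It needs a short SAP amendment, one derived variable and a second run of two outputs. The price is an older baseline for triggered GT005 subjects, so any decline between randomisation and surgery counts in their change. That is already so for GT005 subjects who are not re-measured, but it does not make the arms fully alike, because control Day 1 follows randomisation directly. The sensitivity analysis shows how much this choice matters. The pre-surgery safety check stays as it is.

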### 7.3.10 Best Corrected Visual Acuity

To evaluate changes in visual acuity over the study period, BCVA will be assessed for both eyes using the ETDRS visual acuity chart.

The BCVA test should be performed prior to pupil dilation, and distance refraction should be carried out before BCVA is measured. Initially, letters are read at a distance of 4 metres from the chart. If <20 letters are read at 4 metres, testing at 1 metre should be performed. BCVA is to be reported as number of letters read correctly by the subject. At the Screening Visit, eyes with a BCVA of  $\geq 24$  ETDRS letters (6/95 and 20/320 Snellen acuity equivalent) or better, using ETDRS charts will be eligible for the study.

If a subject cannot read any letters on the BCVA chart, the subject will be tested for finger counting, hand movements or light perception.

### 7.3.11 Low Luminance Difference

To evaluate the subject's low luminance deficit, LLD will be measured for both eyes. The test should be performed after BCVA testing, prior to pupil dilation, and distance refraction should be carried out before LLVA is measured. LLVA is measured by placing a 2.0-log-unit neutral density filter over the front of each eye and having the subject read the normally illuminated ETDRS chart. Initially, letters are read at a distance of 4 metres from the chart in each eye. If <20 letters are read at 4 metres, testing at 1 metre should be performed. The LLD is calculated as the difference between BCVA and LLVA.

### 7.3.12 Reading Performance

Monocular (study eye separate from contralateral eye) Reading Speed will be assessed by the Minnesota Low-Vision Reading Test (MNRead Acuity Test) [Appendix 17.2]. The reading test will be provided in the native language of the participating subject.

